Wait-list control condition: Participants will conduct their lives as usual during the 30-day intervention period.

Screening and Enrollment

Study Participants:

All participants will be 18 years old and above, patients at the UHealth Lennar Foundation Medical Center, and will have no prior or current exposure to the FFW intervention.

The maximum number of subjects we intend to screen is 1,000.

The total number of subjects we intend to enroll is 500.

Exclusion/Inclusion Criteria

The study population will be patients at the UHealth Lennar Foundation Medical Center. The criteria for exclusion of participants are:

- 1) Those under the age of 18
- 2) Those not patients at the UHealth Lennar Foundation Medical Center
- 3) Those who have ever participated in the FFW intervention in another study

Rationale for exclusions: 1) Individuals who are not patients at the UHealth Lennar Foundation Medical Center will be excluded because we would like to generalize findings to patients at the UHealth Lennar Foundation Medical Center.

IRB Study Number: TBD

Title: Patient Well-Being Research Project 01-23-17 to IRB

2) Individuals under the age of 18 will be excluded as the program content and self-assessment tool have been created for an adult population.

3) Individuals who are/have been exposed to the FFW intervention will be excluded to avoid threats to the study's internal validity.

The criteria for inclusion of participants are:

- 1) Adults aged 18 and above
- 2) Those who are patients at the UHealth Lennar Foundation Medical Center.
- 3) Those who have never participated in the FFW intervention in another study.

Background

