30 days has passed from the day each participant was randomly assigned to their group (intervention or control), she/he will be sent an e-mail reminding her/him to return to the website to complete some more surveys and receive an additional \$10 electronic gift card credit. For intervention group participants, those participants who completed at least 50% of each of the 15 modules will also be credited \$15 of Amazon electronic gift cards in their account. After an additional 30 days, each participant will be e-mailed again to return to the website for the last time to complete the final set of surveys and receive the final additional \$15 electronic gift card credit. After each participant has completed the final surveys, she/he will be e-mailed codes to redeem the total amount of Amazon electronic gift cards he/she has been credited throughout her/his Patient Well-Being Research Project experience. In total, each intervention participant will have the opportunity to obtain \$45 worth of Amazon electronic gift cards. Control group participants will have the opportunity to obtain a total of \$30 in Amazon electronic gift cards.

The following italicized text is the message participants will be presented immediately after they complete and submit the 3rd battery set of surveys.

“Thank you for completing this set of surveys. Around [Date] we will send you an email with instructions on how to redeem your Amazon electronic gift codes.”

Participant Recruitment Plan

The study aims to consent (i.e. enroll), assess, and randomly assign no more than 500 participants in a rolling fashion in real-time within an online environment. A timeframe of 24-calendar days will be considered the “recruitment window” to achieve this enrollment aim.

During the recruitment window the following research activities will take place simultaneously across multiple participants: 1) participant recruitment; 2) Patient Well-Being Research Project personal account creation; 3) e-mail validation procedure; 4) screening; 5) consenting; 6) data

IRB Study Number: TBD

Title: Patient Well-Being Research Project 01-23-17 to IRB

collection of baseline (T1) survey battery set; 7) participant incentive #1 credit deposit; 8) participant randomization and condition group assignment; 9) participant-intervention group online program access

[figure not shown]
Recruitment Window Procedures

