Participants will be recruited by being offered a research study invitation flyer, in-person. They will receive the flyer when checking in for their pre-registered medical appointment at the University of Miami's UHealth Lennar Foundation Medical Center. Upon check-in, a clinical access representative will ask each patient if they are interested in receiving an invitation flyer for a research study.

Participant recruitment. The IRB approved study recruitment flyers will begin to be offered to patients at the UM Lennar Medical Center on day 1 of the 24-day recruitment window. See figure 1 below for a visual overview of the real-time recruitment window procedures and communication components:

Figure 1

Recruitment Window

2) Patient Well-Being Research Project personal account request. Each recruited person who wishes to, will have the opportunity to visit the Patient Well-Being Research Project log-in page. To ensure the probability the project is limiting entry to only UM Lennar Medical Center patients who were handed an invitation flyer while on-site at the medical center, each visitor to the log-in page will be immediately prompted to enter a valid code that was printed on the

IRB Study Number: TBD

Title: Patient Well-Being Research Project 01-23-17 to IRB

invitation flyer they were given, in addition to their email address. They will then create a unique username and their own password for their research project account which will be stored in the research project database. All e-mail addresses will be encrypted on the research team's end so the researchers will be blind to the identity of the recruited subjects.

3) E-mail verification procedure and account activation. After respondents have created a personal account, they will receive an automated e-mail delivered to the e-mail address they provided when they created their personal account. They will be prompted to check their e-mail and click on the verification hyperlink to verify their e-mail address and activate the account they created. The salutation field of the automated e-mail verification will be populated with the username the respondent typed in when they requested an account. As soon as they click on the e-mail verification hyperlink, their account will become activated.

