4) Screening. As soon as the verified account holder logs-into the Patient Well-Being Research Project, the respondent will be presented with 3 screening questions to assess inclusion/exclusion criteria. The respondent needs to answer both questions affirmatively to be qualified to move on and read the consent form. Respondents who do not affirm the first two screening questions and/or affirm the third, will be terminated from the study and locked out of further access to the research project website. Below are the screening questions and the messages excluded respondents will receive:

a) Respondent is first asked:

i) Are you at least 18 years old?

yes = will continue to second inclusion/exclusion criterion question

no = will be excluded and blocked from further access to the website and presented with the following message:

“Thank you for your help. At this time it appears you do not meet criteria for the current study. However, future studies and software development

testing will be occurring. Please visit us again at the next opportunity. We sincerely appreciate your time and effort. ”

b) Continuing respondents are asked:

ii) Are you currently a patient at the University of Miami Lennar Foundation Medical Center?

yes = will continue to Consent page

no = will be excluded and blocked from further access to the website and presented with the following message:

“Thank you for your help. At this time it appears you do not meet criteria for the current study. However, future studies and software development testing will be occurring. Please visit us again at the next opportunity. We sincerely appreciate your time and effort. ”

c) Continuing respondents are asked:

iii) Are you now, or have you ever participated in activities of the Fun For Wellness online program?

yes = will be excluded and blocked from further access to the website and presented with the following message:

“Thank you for your help. At this time it appears you do not meet criteria for the current study. However, future studies and software development testing will be occurring. Please visit us again at the next opportunity. We sincerely appreciate your time and effort. ”

no = will continue to Consent page

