Title: Patient Well-Being Research Project 01-23-17 to IRB

represented visually on the user's page as they complete each assessment to show their level of battery completion. Below is the T1 battery set of assessments that all consented participants will be administered prior to being randomized to a condition group.

1. FFW Demographics Questionnaire (9 items)
2. Self-Efficacy to Comply Measure (1 item)
3. I COPPE Scale- 30-day version (21 items)
4. SEWB Scale- 30-day version (21 items)
5. I COPPE Actions Scale- Revised (19 items, including 1 attention filter item)
6. Chronic Conditions Checklist (20 items)
7. SF-36 v2 (36 items)

On day 14 of the recruitment window, a baseline (T1) data collection battery set reminder e-mail will be sent to all consented participants who have not completed T1 data collection letting them know they have 10 more days to complete the T1 battery set of surveys. Here is the e-mail subject line: ***Patient Well-Being Research Project: Reminder to complete Survey Set #1.***

7) Participant incentive #1 credit deposit. After each participant submits the final survey, a visual and sound action will show the \$5 Amazon electronic gift card credit into the participants' Patient Well-Being Research Project bank account.

8) Participant randomization and condition group assignment. Participants who have completed the full T1 battery will be randomly assigned in real time to either the intervention condition or the wait-list control condition. Randomization and assignment will be done solely by the computer program so researchers will be blind to participant randomization and group assignment. The computer program will use a 2:1 randomization algorithm so that there are twice as many intervention participants as control participants. Participants will be randomly assigned based on their sequential order in the assignment line up which will be established at the exact time of each participant's submission of the battery of the first set of surveys (i.e. T1).

IRB Study Number: TBD

Title: Patient Well-Being Research Project 01-23-17 to IRB

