The first participant who submits their T1 battery will be assigned control or intervention based on a digital coin flip. For each additional participant who submits their T1 battery, if we need another person to fulfill the intervention (2:1) ratio, that person will be assigned to the intervention condition. The same with control, if more control participants need to be assigned to that condition, then the participant will be added to the control group. If we already have an exact 2:1 ratio, the participant will be assigned to one of the two conditions based on a digital coin flip.

9) Participant condition group access. As soon as participants complete the T1 battery set of surveys and are randomized by the computer, they will be sent a welcome e-mail. Here is the e-mail subject line: *Welcome to the Patient Well-Being Research Project*.

Intervention participants will have immediate access to the Fun For Wellness and control participants will be wait-listed. Participants in the intervention group may access the Patient Well-Being Research Project site during all hours of the 30-day access window. Control group participants will be informed they have been randomly assigned to the wait-list condition and will be given eventual 30 days of access to the online well-being program at the end of the 60-day study.

After 30 days, participants in the intervention group will no longer have access to the online program at the Patient Well-Being Research Project site. Participants from both condition groups may still log in to see how much credit they have in their account to redeem Amazon electronic gift card codes. Participants in both groups will be sent reminder e-mails to complete the survey set for the second time (T2: 30-days post baseline). After 30 more days have passed (T3: 60-days post baseline), participants will receive reminder e-mails to complete the survey set for the third time.

IRB Study Number: TBD

Title: Patient Well-Being Research Project 01-23-17 to IRB

10) Participant e-mail reminder plan. Two types of e-mail reminders will be automatically sent to participants during the 60-day study period. The first type of e-mail will encourage continued participation in the online program. The second type of email will encourage completion of the surveys.

a) Email to encourage continued participation:

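### The entry rules do not stop a person already randomized in this trial from registering and being randomized a second time

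*Combined protocol and SAP*

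**What the plan says.** The Participant Recruitment Plan sets the window: "A timeframe of 24-calendar days will be considered the “recruitment window” to achieve this enrollment aim". Within it the study will "randomly assign no more than 500 participants in a rolling fashion in real-time within an online environment", with account creation, screening, consent, baseline surveys, assignment and program access all running at once across participants.

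On assignment (Recruitment Window Procedures, item 8): "Participants who have completed the full T1 battery will be randomly assigned in real time", at 2:1. Under item 9 a welcome e-mail follows as soon as a participant is randomized, and "Control group participants will be informed they have been randomly assigned to the wait-list condition", with program access promised after the 60-day study.

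Four elements govern entry:

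- **Flyer code** (item 2, account request): "each visitor to the log-in page will be immediately prompted to enter a valid code that was printed on the" invitation flyer. Flyers are offered to patients at check-in.
- **E-mail** (items 2 and 3): the address is verified by a link. Addresses are encrypted "so the researchers will be blind to the identity of the recruited subjects".
- **Screening** (item 4): three self-reported questions, on age, current patient status, and "Are you now, or have you ever participated in activities of the Fun For Wellness online program".
- **Exclusion 3** (Exclusion/Inclusion Criteria): "Those who have ever participated in the FFW intervention in another study".

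The Data Analysis Plan refers to quality-control procedures established in the team's prior studies. It states no check for duplicate persons and no rule for handling two records from one person.

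**The concern.** Neither the screening questions nor the exclusion criteria ask whether the respondent is already in this trial. A control learns of the wait-list assignment while enrolment may still be open, and a second account offers a chance of immediate access.

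Two things are at stake. The first is contamination: a control who re-enters and is assigned to the program is exposed to it but still answers T2 and T3 as a control, which pulls the arms together. The protocol itself justifies exclusion 3 by internal validity, and this route works against that purpose. The second is double counting: one person supplies two records, in both arms or twice in one arm. Records are then not independent, and the number of distinct people falls below the number enrolled.

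**Working it through.** **Step 1. Trace the screening answers.** Take three people already randomized who return within the window with another e-mail address.

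| Person | Adult? | Current patient? | FFW activities? | Result |
|---|---|---|---|---|
| Wait-listed control | yes | yes | no (no access yet) | goes to consent |
| Intervention, nothing started | yes | yes | no (no activity done) | goes to consent |
| Intervention, started | yes | yes | yes | excluded |

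All of these answers are truthful. Exclusion 3 reaches none of the three, because its wording concerns another study.

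**Step 2. Check the other gates.** The code must be valid, but it is not stated to be unique or single-use. No enrolment check is described when flyers are handed out, so a second flyer is also possible. E-mail verification shows only that an address works. The lock-outs described apply to people who fail screening, decline consent or reject the disclaimer. IP filtering (Data storage methods & data security) protects the database and does not screen registrants.

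**Step 3. Chance that a second account draws intervention.** At a later place in the line it is about 2/3, from the 2:1 ratio. If the second baseline battery is the very next one submitted after the control assignment, it is higher. Item 8 can be read in two ways when the first assignment of a set is intervention:

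- If the next is then control, the sets are I-C-I or C-I-I, and a control is always followed by intervention: 1.00.
- If the next is then a second intervention, the sets are I-I-C or C-I-I with equal chance: 0.5 × 0.5 + 0.5 × 1 = 0.75.

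The figures below use 2/3.

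**Step 4. Illustrative size.** The plan states no re-registration rate, effect size, alpha or power, so there is no figure of its own to reproduce. The re-registration share *f* among controls is assumed.

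- Controls: 500 / 3 ≈ 167.
- Re-registrations: 167 × *f* = 8.4 at 5% and 16.7 at 10%.
- Crossovers: × 2/3 = 5.6 and 11.1, about 6 and 11 people.
- Share of the control arm: *c* = *f* × 2/3 = 3.3% and 6.7%.
- Distinct people among 500 records: 500 − 8.4 ≈ 492 and 500 − 16.7 ≈ 483.

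**Step 5. Illustrative effect on power.** Assume a simple two-mean comparison, two-sided alpha 0.05, SD 1, 333 versus 167, and the full program effect in anyone who crosses. The difference with 80% power is (1.960 + 0.842) × √(1/167 + 1/333) = 0.266. Diluted to 0.266 × (1 − *c*):

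- *f* = 5%: difference 0.257, power 77%.
- *f* = 10%: difference 0.248, power 74%.

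These figures ignore the correlation between two records from one person, and any re-registration by intervention participants.

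**The case against.** The best case against is that this is a gap in what is stated, with no evidence that anyone would use it. Whether codes are unique is not said either way, and the flyer, the consent form and Figure 1 are not in the text reviewed, so a one-registration rule could sit there. The motive is limited: controls are promised 30 days of access later, gift codes are sent only after the final surveys, and a second account means a new consent, another 127-item baseline battery and two more follow-up batteries. One account in each arm could earn up to $30 + $45 = $75, but $15 of that requires at least half of each of the 15 modules. Controls randomized late in the window or near the cap have little or no chance to return. All of this stands. It limits the likely size but does not supply the missing rule.

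Three stronger readings are tempting, and the documents do not support them:

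- *Only controls can do this.* The question asks about activities done, so an intervention participant who has not started can also pass.
- *Duplicates could not be noticed.* The data security section describes a protected list linking e-mail addresses to ID numbers, open to authorized staff, and each person gives demographics and a 20-item conditions checklist at baseline. A repeated address or a close match could be found. What is missing is a stated check.
- *The control arm will be contaminated.* No rate is given anywhere. The 5-10% is an assumption, and it is applied to all controls, including those with little time left to re-enter.

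**Conclusion.** The point holds as a gap in the entry rules. Applied as written, they admit a person who has already been randomized, provided that person uses a second e-mail address while the window and the cap of 500 still allow it. That a control knows the allocation at that time is inferred from the welcome e-mail described immediately before the sentence on informing controls.

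The size is unknown. Under the assumed 5-10%, about 6-11 controls (3-7% of the arm) would cross over, and a comparison with 80% power would fall to about 77-74%. The true figure would be lower if many controls are randomized late, or if those who cross gain less than the full effect. This is a cheap improvement of minor priority, not a threat to the design.

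**What to change.** 1. **Criterion and screening item.** Add an exclusion for anyone already consented or randomized in this project, with a matching item such as: *Have you previously consented to, or been assigned to a group in, the Patient Well-Being Research Project under any other account?* (yes = excluded). Do not ask whether an account has been created: screening comes after account activation, so every first-time respondent would have to say yes. Widening exclusion 3 to cover this study as well as others is not enough, because a wait-listed control has not taken part in FFW.
2. **Flyer code.** Print a unique serial code on each flyer and bind it to one account when that account is activated, so that it cannot open a second.
3. **Duplicate check.** Prespecify a check on e-mail address, flyer code and matching demographics, run by the site or database staff so that the researchers stay blind to identity. Fix the matching rule in advance, and keep only the first randomization. This restores one record per person but cannot undo exposure in a control who has already used the program, so items 1 and 2 are still needed.

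The cost is one screening item, one criterion, serial numbers on the flyers, a used-code check and a short paragraph in the analysis plan. A patient who loses a code before using it needs a new flyer. A second flyer plus a false answer could still get through, which is why item 3 is needed as well.

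### The 2:1 allocation rule puts one arrival position in every three always in the intervention arm, so about a third of participants have no chance of control

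*Combined protocol and SAP*

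**What the plan says.** The rule is in the combined protocol and SAP, Study Procedures, item 8 (Participant randomization and condition group assignment). It opens with the claim of randomization: "Participants who have completed the full T1 battery will be randomly assigned in real time". The target ratio follows: "The computer program will use a 2:1 randomization algorithm so that there are twice as many intervention participants as control participants". Order matters: "Participants will be randomly assigned based on their sequential order in the assignment line up", and the line-up is fixed by the time of T1 submission. On concealment: "Randomization and assignment will be done solely by the computer program so researchers will be blind" to the result.

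The next paragraph gives the mechanism. The first participant is assigned by a digital coin flip. After that, "if we need another person to fulfill the intervention (2:1) ratio, that person will be assigned to the intervention condition". For the other arm: "The same with control, if more control participants need to be assigned to that condition", the participant goes to control. Finally, "If we already have an exact 2:1 ratio, the participant will be assigned to one of the two conditions", again by coin flip.

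The sample size comes from the Participant Recruitment Plan: "The study aims to consent (i.e. enroll), assess, and randomly assign no more than 500 participants in a rolling fashion". Screening and Enrollment gives 500 as the intended enrolment.

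**The concern.** Chance enters only at the first participant and at an exact 2:1 split. Everyone else is placed by need. A 2:1 scheme should give each participant a 2/3 chance of intervention before the sequence is drawn. A 50:50 coin followed by forced filling cannot do that, so the 2:1 totals must come from participants who are placed in the intervention arm without any chance element.

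There is also a gap in the text. After a first assignment to intervention (1:0), reaching 2:1 takes one more intervention participant and one more control. Both need clauses can then apply, and neither is given priority. The same state recurs at 3:1, 5:2 and so on.

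Two things are at stake. A report that all participants were randomized would be inaccurate for those in the fixed positions. And two programmers could build different sequences from the same paragraph.

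**Working it through.** **Inputs.** Ratio 2:1, assignment in order of submission, and the coin-flip and need rules, all from item 8; N = 500 from the Participant Recruitment Plan. Assumption: the coin is 50:50, which the text does not state.

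**Triplets.** Write I for intervention and C for control. Every third assignment returns the split to exactly 2:1, so the sequence is a chain of triplets, each starting with a coin flip.

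- Flip gives C (0:1): the next two must be I. Order: C,I,I.
- Flip gives I (1:0), running-ratio reading: 1:0 exceeds 2:1, so control is next, then intervention. Order: I,C,I.
- Flip gives I (1:0), fill-the-triplet reading: intervention has not reached its two, so intervention is next, then control. Order: I,I,C.

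**The plan's own target.** 500 = 166 triplets (498 participants, 332:166) plus two more.

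- Running-ratio: the last two are C,I or I,C, giving 333:167.
- Fill-the-triplet: the last two are C,I or I,I, giving 333:167 or 334:166, each with probability 1/2.

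The 2:1 target is therefore reproduced under both readings.

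**Chance of intervention by position.**

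| Scheme | 1st | 2nd | 3rd |
|---|---|---|---|
| Written rule, running-ratio (CII or ICI) | 1/2 | 1/2 | 1 |
| Written rule, fill-the-triplet (CII or IIC) | 1/2 | 1 | 1/2 |
| Permuted block of 3, all three orders equally likely | 2/3 | 2/3 | 2/3 |

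**Participants with no chance of control.**

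- Running-ratio: positions 3, 6, ..., 498, which is 498/3 = 166 (33.2% of 500; 166/333 = 49.8% of the intervention arm).
- Fill-the-triplet: positions 2, 5, ..., 500, which is (500 − 2)/3 + 1 = 167 (33.4% of 500; about half of the intervention arm).

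The remaining 334 (500 − 166) or 333 (500 − 167) split 167:167, or 166:167 or 167:166. In effect the rule randomizes these 1:1, in pairs where one member mirrors the other's coin flip, and then adds the fixed intervention places.

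**Predictability (secondary).** There are 167 coin flips (positions 1, 4, ..., 499), so 500 − 167 = 333 assignments (66.6%) follow from the counts. Someone who knew the counts would guess correctly (0.5 + 1 + 1)/3 = 83.3% of the time. For permuted blocks of 3 the success rate is (2/3 + 2/3 + 1)/3 = 77.8%, with (0 + 1/3 + 1)/3 = 44.4% forced. Blocks of 3, 6 and 9 in random order, sizes unknown to the guesser, gave 73.7% in 400 simulated lists of 500. Independent 2/3 draws give 66.7%.

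**The case against.** The strongest reply is that the fixed position depends on how the gap at 1:0 is filled. If a programmer flips a coin there because both arms are short, the chances become 1/2, 3/4 and 3/4, and no position is fixed. But the text allows a flip only for the first participant and at exact 2:1, so this needs a step it does not supply, and the chances are still unequal. One can also argue that the intervention clause comes first and so points to the fill-the-triplet version. That would settle the ambiguity but leave the second position fixed.

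Second, item 8 openly says that order of arrival determines assignment. That discloses the dependence, but the same sentence still calls the assignment random.

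Third, forced assignments occur in any permuted block, and predictability matters only if someone who sees the counts can influence entry. The documents describe no such person: screening, consent and T1 are completed online, the computer assigns afterwards, and researchers are stated to be blind. This stands. The predictability figures are secondary, and the defect is the zero chance of control at one position. Nor is any link shown between position in a triplet and prognosis, so no bias can be quantified.

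Fourth, 500 is a ceiling. If fewer are assigned, the count is about one third of the actual number.

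**Conclusion.** The concern holds. Followed as written, the rule meets the 2:1 group sizes but gives 166 or 167 of 500 participants, about one third, no chance of control. This is so under both deterministic readings of the paragraph, and it contradicts the plan's own statement of random assignment. The paragraph is also ambiguous whenever the intervention arm is one ahead of 2:1.

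The result rests on a 50:50 coin and on coin flips occurring only where the text places them. It is a design weakness that should be fixed before the first assignment, because it cannot be repaired afterwards. It is not evidence of selection bias, and the documents give no basis for estimating any effect on the results.

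**What to change.** Before the first assignment, delete the coin-flip and need-based text in item 8 and replace it with, for example:

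> At T1 submission the computer assigns each participant from a concealed, computer-generated list of permuted blocks, with block sizes drawn at random from 3, 6 and 9, two intervention places for each control place, and all orders within a block equally likely.

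Independent draws with a 2/3 chance of intervention are an acceptable alternative. Blocks of 3 with all three orders equally likely would also cure the central defect; the mixed sizes only reduce predictability. Each option gives every participant a 2/3 chance and removes the ambiguity at 1:0.

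Changing only the coin to 2/3 does not repair the rule: the chances by position become 2/3, 1/3, 1 or 2/3, 1, 1/3, and one position stays fixed.

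The cost is one protocol paragraph and a small code change. With 3/6/9 blocks, an incomplete last block leaves 332 to 335 intervention participants of 500. With independent draws the standard deviation of the intervention count is √(500 × 2/3 × 1/3) = 10.5 participants.
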